 - b. Vasopressor infusion titrations according to protocol are recommended, while clinicians retain the ability to titrate as they feel clinically indicated. Norepinephrine should be the primary vasopressor; at 0.25 mcg/kg/min of norepinephrine, a second vasopressor agent (preferentially, vasopressin 0.03 units/min or epinephrine) may be added; at 0.5 mcg/kg/min, stress-dose steroids (hydrocortisone 150-200 mg IV daily or equivalent, in divided doses) may be added.

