 - a. For the esmolol titration protocol, each hour (the closest value of heart rate to the hour) during the esmolol infusion will be determined to be “in range” or “out of range,” with 3bpm margin for compliance (i.e., heart rate 77 to 93bpm). The initiation and cessation of esmolol will also be included as a timepoint for evaluation of compliance. Protocol compliance is considered adequate where overall compliance on hourly checks is >80%.
 - b. For STOP events, protocol compliance is considered adequate at 100%.
 - i. 30min moving average of cardiac index below threshold
 - ii. 30min moving average of norepinephrine infusion rate above threshold
 - iii. Clinician determines that shock has substantially worsened on esmolol.

- c. For VOLUME EXPANSION events, protocol compliance is considered adequate at 90%.
- 4. Amount of research coordinator time spent on different tasks

2.8.1 Anticipated primary clinical outcome for main trial (this will also be recorded for ROLLIN): Organ-failure-free days at 28 days. An organ-failure-free day is defined as a calendar day on which the patient receives none of (a) vasopressor therapy, (b) mechanical ventilation, or (c) renal replacement therapy.

2.8.2 Anticipated secondary clinical outcomes for main trial (these will also be recorded for ROLLIN):

1. All-cause hospital mortality
2. All-cause 28-day and 90-day mortality
 - a. Mortality will be ascertained through telephone followup for patients who were discharged alive before 90 days.
3. Peak serum high-sensitivity troponin
 - a. Troponin will be measured on day 0 and day 1.
4. LV global longitudinal strain at 24 hours
5. Time to transition to quiescent vascular phenotype, as defined by serum Angpt-2 level < 1ng/ml.
6. ICU-free days to day 28
 - a. Patients who die before 28 days will be assigned -1 ICU-free days, using a methodology similar to that used for organ-failure-free days.
7. Cardiogenic shock/requirement for inotropes through day 14. This is a binary variable and is met when any of the following is present
 - a. Dobutamine or milrinone infusion at any dose, lasting > 60min
 - b. $CI \leq 2$ L/min/m² lasting > 30 min on NICOM
 - c. $ScvO_2 \leq 60\%$ on any measurement
8. Development of second or third degree heart block.

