4.2 Inclusion Criteria

Subjects will be considered eligible for the study when they are older than 18 years of age, admitted to an ICU with septic shock, and for at least an hour, they are receiving vasopressors through a central venous catheter and have a heart rate > 90/min. Subjects must meet the heart rate and vasopressor criteria at the time of enrollment.

Inclusion Criterion	Justification/Description
Age ≥ 18 years	Children are physiologically distinct from adults
Septic shock	Meets consensus criteria: 
 ≥2 SIRS criteria Suspected or confirmed infection Receiving vasopressor infusion to treat hypotension after at least 20ml/kg intravenous crystalloid volume expansion
Adequately volume expanded	Designed to include only non-compensatory tachycardia, that which persists after adequate volume expansion. Being no longer fluid responsive requires any one of 
 CVP > 15 mmHg Negative Passive Leg Raise (PLR) maneuver (< 10% increase in cardiac output during PLR) Stroke volume increase < 10% in response to rapid (< 5 min) infusion of at least 250 ml crystalloid solution In patients being passively mechanically ventilated, stroke volume variability (measured by a valid method, including NICOM) < 10%
Receiving vasopressor infusion via central venous catheter	At least 60 min of any infusion rate of norepinephrine, epinephrine, vasopressin, or phenylephrine
Current or imminent placement of arterial catheter	Allows continuous measurement of blood pressures during esmolol infusion and is standard in the study ICU.
Tachycardia (>90/min)	Heart rate must remain > 90/min for at least one hour, while the patient is receiving vasopressors

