ECASSS ROLL-IN Study Drug Titration protocol

Fundamental rules for study drug titration:

The target heart rate is 85 bpm. Start study drug infusion at 20 mcg/kg/min, without bolus, if HR \geq 100 bpm. If HR >90 bpm and <100 bpm, start study drug infusion at 10 mcg/kg/min, without bolus. Increase by 20 mcg/kg/min every 20 minutes as long as HR > 90 bpm, to a maximum dose of 100 mcg/kg/min. If HR < 80 bpm and > 70 bpm, decrease infusion rate by 10 mcg/kg/min; if HR ≤ 70 bpm and > 60 bpm, decrease infusion rate by 20 mcg/kg/min. Stop study drug infusion whenever a STOP EVENT occurs. Study drug infusion is completed 3 hours after vasopressor infusions have stopped. The up-titrations can be smaller than stipulated if the clinician and/or investigator feels that a small up-titration is indicated. Up-titrations should not occur during a REASSESS VOLUME STATUS event.

Study drug should be preferentially infused centrally; where no port is available, study drug should **not be** infused into a small peripheral vein or via butterfly catheter.

STOP EVENTS:

1. If HR is ever ≤ 60 bpm, immediately stop infusion for 20 minutes, then restart at half the previous infusion rate, rounded to nearest 10 mcg/kg/min. Do not resume infusion until HR > 70 bpm.
2. If vasopressor dose increases by 0.2 mcg/kg/min norepinephrine (or equivalent) AND doubles within 60 min despite adequate volume expansion, STOP the study drug infusion. Alternatively, if the treating clinician believes that the shock is worsening significantly, STOP the study drug infusion. Do not resume without explicit approval of study physician.
3. If cardiogenic shock develops ($ScvO_2 \leq 60\%$ OR LV Ejection Fraction $\leq 25\%$ OR Cardiac Index ≤ 2.0 L/min/m²), STOP the study drug infusion. Do not resume without explicit approval of study physician.
4. If clinically apparent bronchospasm develops, STOP the study drug infusion. Do not resume.
5. If Grade 2 or Grade 3 heart block develops, immediately STOP the study drug infusion. Do not resume.

REASSESS VOLUME STATUS EVENTS:

When markers of potential preload deficit occur (urine output < 0.5 ml/kg/hr OR vasopressor dosage increase), immediately EVALUATE FOR VOLUME RESPONSIVENESS. A vasopressor dosage increase is defined as at least 0.05 mcg/kg/min absolute AND 20% relative increase in the norepinephrine (or equivalent) infusion.

Titrate vasopressors as per local practice to maintain MAP ≥ 65 mmHg. Norepinephrine is the preferred primary vasopressor.

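### The vasopressor STOP rule in Appendix 1 and its compliance score in section 2.8 use different quantities and time windows, and the norepinephrine equivalent behind the rule is undefined

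*Combined protocol and SAP*

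**What the plan says.** Appendix 1, STOP EVENTS item 2, has two limbs. The numeric one is: "If vasopressor dose increases by 0.2 mcg/kg/min norepinephrine (or equivalent) AND doubles within 60 min despite adequate volume expansion, STOP the study drug infusion". The other rests on judgement: "Alternatively, if the treating clinician believes that the shock is worsening significantly, STOP the study drug infusion".

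The vasopressor trigger under REASSESS VOLUME STATUS EVENTS is a rise of "at least 0.05 mcg/kg/min absolute AND 20% relative increase in the norepinephrine (or equivalent) infusion". Its effect on esmolol is indirect: "Up-titrations should not occur during a REASSESS VOLUME STATUS event". Low urine output triggers the same reassessment by itself.

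Agents other than norepinephrine are expected. Section 2.4 item 4b says that, at norepinephrine 0.25 mcg/kg/min, "a second vasopressor agent (preferentially, vasopressin 0.03 units/min or epinephrine) may be added". Section 4.2 accepts as the qualifying vasopressor "At least 60 min of any infusion rate of norepinephrine, epinephrine, vasopressin, or phenylephrine".

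Section 2.8 item 3b lists the STOP events to be scored for protocol compliance, which is adequate only at 100%. The vasopressor item reads "30min moving average of norepinephrine infusion rate above threshold". It has no equivalence clause and states no threshold. The other two items are a moving average of cardiac index and the clinician's judgement that shock has substantially worsened.

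The readable text contains no conversion for epinephrine, phenylephrine or vasopressin. Some figures are not reproduced. Figures 1 and 2 deal with inclusion screening and the final safety check, so a conversion there is unlikely but cannot be excluded.

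**The concern.** A dose rule stated in equivalents can be applied in only one way if the equivalence is stated. Vasopressin makes the gap plain: it is given in units/min, not per kilogram, so bedside staff cannot infer its norepinephrine value from the units.

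The second difficulty is that the plan does not score the rule it tells staff to follow. Appendix 1 asks for a rise and a doubling within 60 minutes, counted across agents. Section 2.8 asks for a 30-minute average of norepinephrine alone, above some level. A report of 100% STOP compliance could therefore coexist with a missed Appendix 1 STOP that was reached on another agent. Equally, staff who followed Appendix 1 correctly could be scored as non-compliant.

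Sections 3.3 and 7.2 make protocol adequacy and compliance the purpose of this roll-in. With up to 10 patients and a 100% standard, one misclassified STOP decides whether the standard is met.

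**Working it through.** The plan has no figure of its own to reproduce here. The check applies both triggers as written while the undefined conversion varies.

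**Inputs from Appendix 1.** Let b and a be the vasopressor dose before and after, in mcg/kg/min of norepinephrine or equivalent.
- STOP event 2, numeric limb: a − b ≥ 0.2 and a/b ≥ 2, within 60 minutes.
- Reassess trigger: a − b ≥ 0.05 and (a − b)/b ≥ 0.20.

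**Assumptions, not in the documents.** e is the norepinephrine equivalent of vasopressin 0.03 units/min, varied from 0 to 0.20 mcg/kg/min. k is the conversion factor for phenylephrine, varied from 0.05 to 1.0. All changes fall within 60 minutes and volume expansion is adequate. The dose paths and values are illustrations, not proposals.

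**Case 1: norepinephrine 0.25 to 0.40, vasopressin newly added.** Rise = 0.15 + e; ratio = (0.40 + e)/0.25.

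| e | Rise | Ratio | Numeric STOP |
|---|---|---|---|
| 0 | 0.15 | 1.60 | no |
| 0.05 | 0.20 | 1.80 | no |
| 0.10 | 0.25 | 2.00 | yes |
| 0.15 | 0.30 | 2.20 | yes |

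Doubling is the binding condition: 0.40 + e ≥ 0.50 gives e ≥ 0.10.

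**Case 2: norepinephrine 0.20 to 0.40, vasopressin running throughout.** Rise = 0.20 whatever e is; ratio = (0.40 + e)/(0.20 + e).

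| e | Rise | Ratio | Numeric STOP |
|---|---|---|---|
| 0 | 0.20 | 2.00 | yes |
| 0.05 | 0.20 | 1.80 | no |
| 0.10 | 0.20 | 1.67 | no |

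Doubling needs 0.40 + e ≥ 0.40 + 2e, which fails for every e above 0.

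**Case 3: norepinephrine flat at 0.25, vasopressin newly added.** Rise = e; relative rise = e/0.25. Both conditions are met when e ≥ 0.05 (0.05/0.25 = 20%). Below that there is no dose-based reassess event, so that trigger does not bar a further rise in esmolol.

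**Case 4: phenylephrine alone, 1.0 to 2.0 mcg/kg/min.** Rise = k; ratio = 2. The numeric STOP needs k ≥ 0.20; the reassess trigger is met at every k from 0.05. Counting norepinephrine only, the dose is zero before and after, and a doubling is undefined.

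**Against the section 2.8 score.** Section 2.8 gives no threshold, so suppose that the Appendix 1 limits carry over and that the 30-minute average has caught up with the new rate.
- Case 1: the scored quantity rises by 0.15 (×1.60), so no STOP is scored. If e ≥ 0.10, Appendix 1 required one.
- Case 2: the scored quantity rises by 0.20 (×2.00), so a STOP is scored. If e is above 0, Appendix 1 did not require one.
- Case 4: the scored quantity is zero throughout, so no numeric STOP can be scored. If k ≥ 0.20, Appendix 1 required one.

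The two rules can thus disagree in either direction. Carrying the limits over is itself a guess: Appendix 1 limits a change and a ratio, whereas section 2.8 refers to a rate above a level.

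**The case against.** The strongest answer is that esmolol does not depend on this arithmetic. The clinician limb of STOP event 2 needs no conversion, section 2.8 includes it among the scored STOP events, and a team adding a second vasopressor is well placed to use it. STOP event 3 sets numeric limits on ScvO₂, ejection fraction and cardiac index, and section 8.2.1 describes continuous cardiac output monitoring. Urine output can trigger the volume reassessment alone. The safety committee reviews at 3 and 6 patients. All of this stands. A reader might infer that a patient whose shock worsens on a second agent would be left on esmolol; the documents do not support that. They support only that the numeric limb is indeterminate.

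The equivalence wording also signals that other agents count, so e = 0 fits it poorly. That stands too, but it leaves the size of e open: Case 1 turns on whether e reaches 0.10, and Case 2 fails at any positive value.

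As written, the section 2.8 score needs no conversion, because it names norepinephrine only. That is correct, and it is why the defect is a mismatch between rule and score, not an ambiguity within the score.

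Finally, a reader might see a contradiction between the protocolised titration recommended in section 2.4 and the Appendix 1 instruction "Titrate vasopressors as per local practice to maintain MAP" at or above 65 mmHg. Section 2.4 leaves clinicians free to titrate as they judge, and both places prefer norepinephrine, so the two are compatible.

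**Conclusion.** The point holds as a defect of definition and scoring. The numeric limb of STOP event 2 and the vasopressor reassess trigger cannot be applied reproducibly once an agent other than norepinephrine is running or added. The 100% STOP-compliance standard is assessed on a different quantity and window from the bedside rule.

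The number of patients affected cannot be given, because the documents do not say how many will receive other agents. Patients on norepinephrine alone are unaffected by the equivalence gap, although the 60-minute and 30-minute windows and the missing threshold still apply to them. The switching points (0.10 in Case 1, anything above 0 in Case 2, 0.05 in Case 3, a factor of 0.20 in Case 4) are exact for the paths shown, but those paths and the range of equivalents are assumptions.

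A reader might infer that counting other agents can only add STOP events. Case 2 shows that it can also remove them, so neither way of counting is uniformly the more cautious.

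**What to change.** The sponsor should reconcile section 2.4 item 4b, section 2.8 item 3b, section 4.2 and Appendix 1 so that:
- one defined vasopressor quantity is used for STOP event 2, the reassess trigger and STOP-compliance scoring;
- STOP event 2 and its score use the same time window, and section 2.8 states its threshold;
- the text says how agents other than norepinephrine are counted, and whether starting a second agent is a dose increase.

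Which rule to adopt, and any conversion values, are for the sponsor's clinicians.

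The text change is short; the data collection may cost more. Sections 5.1.3 and 5.1.4 list vasoactive agents and rates at baseline and 24 hours, but the on-treatment list in section 5.1.5 does not. Time-stamped rates of all vasopressors during the infusion may therefore have to be recorded. The number of STOP or reassess events counted may rise or fall.

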2.6 Exclusion criteria

1. Lack of informed consent.
2. Currently receiving ECMO.
3. Known pregnancy or nursing.
4. Patient is a prisoner.
5. Patient on hospice (or equivalent comfort care approach) at or before the time of enrollment.
6. Known or current atrial fibrillation.
7. Previously enrolled in the trial.
8. Known allergy to esmolol or vehicle (see Appendix 2 for BREVIBLOC vehicle ingredients).
9. Receipt of nodal blocking agents (see Appendix 3 for list of such agents) within three half lives
10. Hemoglobin $<$ 7 gm/dl.
11. Cardiac arrest within 24 hours.
12. Pulmonary hypertension (moderate or severe), from documented history of prior right heart catheterization or current evidence on TTE of **any** of the following
 - mPAP \geq 35mmHg

- SPAP \geq 60mmHg
13. Cardiovascular collapse, as manifested by inability to achieve a MAP of 65 mmHg with vasopressor therapy.
 14. Cardiogenic shock, as defined by **any** of the following
 - Cardiac index \leq 2 L/min/m²
 - Ejection fraction \leq 25%
 - ScvO₂ \leq 60%
 - Current infusion of any dose of dobutamine, milrinone, or dopamine
 - Current infusion of epinephrine for clinically diagnosed cardiogenic shock
 15. Significant atrioventricular dysfunction
 - Sick sinus syndrome
 - PR interval > 200 msec
 - Current evidence or prior history of Grade 2 or Grade 3 heart block
 - Pacemaker or plans to place a pacemaker
 16. Pheochromocytoma or status asthmaticus
 17. Receiving clonidine, guanfacine, or moxonidine
 18. Hemoglobin < 7 gm/dl
 19. Cardiovascular collapse (failure to achieve MAP of 65mmHg)
 20. Cardiac arrest within 24 hours
 21. Worse than moderate aortic stenosis
 - Known aortic stenosis, with any of (1) mean gradient \geq 40 mmHg OR (2) maximum gradient \geq 60mmHg OR (3) aortic valve area \leq 1.0cm² OR (4) aortic valve area index \leq 0.85cm²/m² body surface area.
 22. Worse than mild mitral stenosis
 - Known mitral stenosis, with any of (1) valve area \leq 1.5 cm² OR mean gradient \geq 5 mmHg.

2.7 Sample size: The study will enroll up to 10 patients at 1 center.

2.8 Non-clinical outcomes for ROLL-IN:

1. Proportion of eligible patients consented
2. Proportion of compliance with final safety check
 - a. Protocol compliance is considered adequate where compliance is 100% for the safety check.
3. Proportion of protocol compliance

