4.3.1 List of Exclusions and Reason for Exclusions

Exclusion Criterion	Justification/Description
Cardiogenic shock	Safety consideration: β -blockade may worsen preexisting cardiogenic shock. Cardiogenic shock defined as any one of 
 Cardiac Index ≤ 2 L/min/m² ScvO₂ $\leq 60\%$ Ejection Fraction $\leq 25\%$ Current infusion of any dose of dobutamine, milrinone, or dopamine Current infusion of epinephrine to treat clinically diagnosed cardiogenic shock.
Preexisting heart block	Safety consideration: β -blockade may worsen heart block. Defined as any of the following 
 Sick sinus syndrome PR interval > 200 msec Any current evidence or history of Grade 2 or Grade 3 heart block Pacemaker or plans to place a pacemaker
Atrial fibrillation at time of enrollment	Substantial noise associated with exposure, hemodynamic measurements, and outcomes; may require independent heart rate control or cardioversion.
Current nodal blockers or anti-arrhythmic agents	Safety consideration: risk of excess nodal blockade. Increased experimental noise. Receipt of any of the following within 3 half lives (see full list in Appendix) 
 Non-dihydropyridine calcium channel blockers Digitalis Anti-arrhythmics (e.g., amiodarone, dronedarone, mexiletine) Beta blockers
Receiving clonidine, guanfacine, or moxonidine	Safety issue
Moderate or severe pulmonary hypertension	Possible safety consideration; risk of hemodynamic deterioration. Defined as a documented history of prior right heart catheterization or current evidence on TTE of any of the following. 
 mPAP ≥ 35 mmHg SPAP ≥ 60 mmHg
Allergy to esmolol or vehicle	Rare, but required for patient safety.
Admitted for hospice or comfort care	Incomplete and biased data on both exposure and outcome.
Inability to obtain consent within 48 hours of ICU admission	This study does not qualify for waiver of consent
Active pregnancy or nursing	Physiology of pregnant patients distinct; potential risks to fetus unknown; drug levels in breast milk.
Prisoners	Septic shock is not specific to prisoners, so ethical concerns emphasize the protection of autonomy.
Previously enrolled in this trial	Violation of the independence assumption.
Pheochromocytoma or status asthmaticus	Safety issue associated with beta blockade

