8.2 Risk abatement strategies

8.2.1 Cardiogenic shock. As indicated above, patients with preexisting cardiogenic shock are excluded from enrollment, and after enrollment a formal evaluation to exclude cardiogenic shock will be performed before esmolol infusion. The esmolol titration protocol incorporates continuous monitoring of cardiac output using the non-invasive NICOM™ device, and in the rare situation that cardiogenic shock should ensue, esmolol titration will be discontinued and appropriate supportive measures will be instituted. Our use of a no-bolus, slow upward titration protocol for the esmolol infusion is specifically designed to avoid this potential complication.

8.2.2 Excessive bradycardia and/or hypotension. As indicated above, patients with preexisting conduction system disease are excluded from enrollment, and a formal evaluation to exclude conduction system disease will be performed before esmolol infusion. In the event that hypotension or excessive bradycardia should ensue during esmolol infusion, esmolol will be discontinued and appropriate supportive measures will

be instituted. Our use of a no-bolus, slow upward titration protocol for the esmolol infusion is specifically designed to avoid this potential complication.

8.2.3 Hypersensitivity reaction. This is extremely rare. Patients with known hypersensitivity to esmolol or vehicle are excluded from the study. Should this occur, esmolol infusion will be stopped and appropriate treatment measures will be instituted. The short half-life of esmolol avoids concerns about treatment of anaphylaxis in patients on β -blockers, should anaphylaxis occur.

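### STOP event 3 leaves out the inotrope criterion that defines cardiogenic shock at entry, so starting dobutamine, milrinone or dopamine at a cardiac index above 2.0 triggers no objective stop

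*Combined protocol and SAP*

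**What the plan says.** **At entry.** Section 2.6 item 14 and the table in 4.3.1 define cardiogenic shock as any one of five criteria. Three are measurements: CI at or below 2 L/min/m², ejection fraction at or below 25%, and ScvO2 at or below 60%. Two are drug criteria: "Current infusion of any dose of dobutamine, milrinone, or dopamine" and, in the wording of 4.3.1, "Current infusion of epinephrine to treat clinically diagnosed cardiogenic shock".

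**During the infusion.** Appendix 1, STOP event 3, opens "If cardiogenic shock develops" and then lists the same three measurements at the same thresholds. It contains no drug criterion. Resumption needs explicit approval from the study physician.

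**Other protections.**
- STOP event 2 has a vasopressor limb: a rise of 0.2 mcg/kg/min norepinephrine or equivalent together with a doubling within 60 minutes. It also has a judgment limb: "Alternatively, if the treating clinician believes that the shock is worsening significantly, STOP the study drug infusion".
- On monitoring, 8.2.1 states: "The esmolol titration protocol incorporates continuous monitoring of cardiac output". It adds that "in the rare situation that cardiogenic shock should ensue, esmolol titration will be discontinued".
- Section 8.2.2 states: "In the event that hypotension or excessive bradycardia should ensue during esmolol infusion, esmolol will be discontinued". Section 2.4 item 3b also names hypotension as a reason to stop.
- On dose increases, Appendix 1 says: "Up-titrations should not occur during a REASSESS VOLUME STATUS event".

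**The concern.** The protocol uses one term with two definitions. A patient already on dobutamine may not start esmolol, and 4.3.1 gives safety as the reason. A patient put on dobutamine while esmolol is running meets no trigger on that account.

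This matters because of what an inotrope does. It is given to raise cardiac output, so once it is running, CI may stay above 2.0. CI is the only one of the three STOP event 3 measurements described as continuous. The treatment for the suspected problem can therefore keep the automatic stop from firing, while the titration rule still calls for more beta-blocker as long as heart rate is above 90.

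The purpose of the roll-in is to test whether the protocols are adequate before a larger multi-center trial (2.2, 7.2). A gap in a stopping rule is best closed at this stage.

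**Working it through.** No figure in the plan needs reproducing. The check compares the definitions and then follows one patient through the rules.

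**1. Criteria side by side.**

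| Criterion | Exclusion 14 / 4.3.1 | STOP event 3 |
|---|---|---|
| CI ≤ 2 L/min/m² | yes | yes |
| LVEF ≤ 25% | yes | yes |
| ScvO2 ≤ 60% | yes | yes |
| Dobutamine, milrinone or dopamine, any dose | yes | no |
| Epinephrine for clinically diagnosed cardiogenic shock | yes | no |

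STOP event 3 keeps 3 of 5 criteria. The point made here concerns the fourth row. The fifth already rests on a clinical diagnosis, and epinephrine is a permitted second vasopressor (2.4 item 4b), so it could not serve as an objective trigger in the same way.

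**2. Does any other rule fire when an inotrope is started?**
- STOP events 1, 4 and 5 concern heart rate at or below 60, bronchospasm and heart block. None refers to inotropes.
- The vasopressor limb of STOP event 2 is expressed in norepinephrine or equivalent. The vasopressors named in 4.2 are norepinephrine, epinephrine, vasopressin and phenylephrine. Appendix 1 gives no conversion for any agent. Dopamine might be counted as an equivalent; dobutamine and milrinone have no evident place there.
- The judgment limb of STOP event 2 fires if the clinician believes shock is worsening significantly. Starting an inotrope is not itself the trigger.
- Section 2.8 item 3b, which scores STOP compliance, lists CI, norepinephrine rate and clinician determination. It has no inotrope entry.

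**3. Which measurements are available during the infusion?** CI is continuous (8.2.1), so it cannot be treated as missing. ScvO2 is placed at the final safety check (2.4 item 2, 5.1.1.2). Echocardiography is placed at baseline and 24 hours (5.1.3, 5.1.4). The on-treatment list in 5.1.5 names none of the three. A later schedule could sit in a figure that is not reproduced in the text reviewed. ScvO2 can be drawn when wanted, because every patient has a central venous catheter (2.5 item 3).

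**4. Following a patient through.** Take an illustrative CI of 2.2 L/min/m² when dobutamine is started, with no low ScvO2 or LVEF on record and heart rate above 90.
- CI 2.2 > 2.0, so STOP event 3 does not fire. If dobutamine raises or holds CI, it continues not to fire.
- Appendix 1 calls for increases of 20 mcg/kg/min every 20 minutes while heart rate exceeds 90, up to 100 mcg/kg/min. In one hour that is 60 / 20 = 3 increases, or 3 × 20 = 60 mcg/kg/min, subject to the cap. Smaller steps are allowed at the clinician's or investigator's discretion, and none may be taken during an active REASSESS event.
- The infusion stops only if the clinician judges shock to be worsening significantly, hypotension occurs, or another trigger is met independently.

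If instead CI falls to 2.0 or below before the inotrope is started, STOP event 3 fires first and the gap does not arise.

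**The case against.** The case for leaving the rule alone is substantial.

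- **Three measurements may be intended.** The post-enrollment check in 5.1.1.2 evaluates cardiogenic shock by LVEF, ScvO2 and CI, as STOP event 3 does. At screening no study procedure is allowed, so a running inotrope could stand in for missing measurements. The protocol does not give this reason, but the match makes it unsafe to call the omission an oversight.
- **Entry rules are stricter than stop rules elsewhere.** A PR interval above 200 msec bars entry, yet only Grade 2 or 3 block stops the drug. Atrial fibrillation and hemoglobin below 7 gm/dl bar entry and have no STOP event. That a patient would have been excluded does not by itself show the stop rule to be wrong. This stands.
- **The judgment limb is mandatory and scored.** Once the clinician holds the belief, stopping is required, and 2.8 item 3b sets 100% compliance. The treating team also decides on inotropes, so what remains is a clinician who starts one without concluding that shock has worsened significantly. This stands and narrows the gap considerably.
- **Dopamine may be used as a vasopressor.** A trigger at any dose would then stop esmolol for a reason unrelated to cardiac output. This stands as a cost of the fix.

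Two stronger readings are tempting. A reader might infer that esmolol runs unprotected once an inotrope is started. The documents do not support that, given continuous CI, the judgment limb and the hypotension stop. The hypotension stop appears in 2.4 and 8.2.2 but is not itemized in Appendix 1.

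A reader might also infer a contradiction with secondary outcome 7a (2.8.2, 3.5.3), which dobutamine or milrinone for more than 60 minutes can satisfy while esmolol is still running. That outcome covers cardiogenic shock or a requirement for inotropes, and 7a fits the second part. An outcome counted through day 14 is not a stopping rule, so there is no contradiction.

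What the objection does not remove is the masking step. An inotrope started at CI above 2.0 may hold CI above the only continuous trigger, and stopping then rests on judgment or on hypotension.

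**Conclusion.** The gap is real but narrow. It needs an inotrope started during the infusion, CI above 2.0 up to that moment, no ScvO2 or LVEF result at or below threshold, no hypotension, and no clinician judgment that shock is worsening significantly. Up-titration further needs heart rate above 90 and no active REASSESS event.

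The documents give no frequency for inotrope starts during the infusion, so the number of patients affected cannot be estimated. The ceiling in this study is its enrollment of up to 10, with safety committee review after 3 and 6 patients.

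The conclusion assumes that an inotrope can keep CI above threshold, which follows from its purpose but is not quantified in the plan. It also assumes that the figures not reproduced add no inotrope stop. On that footing this is a worthwhile, inexpensive improvement to a safety rule; the rule as written is not an error.

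**What to change.** Add one clause to Appendix 1, STOP event 3: *OR start of dobutamine, milrinone or dopamine at any dose*. Keep the existing condition that the infusion resumes only with explicit study physician approval. Add one line to 2.8 item 3b so that this trigger is scored with the other STOP events.

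The new trigger is objective and time-stamped, and stopping for it is reversible: the protocol relies on esmolol's short half-life (8.1), and approval can restart the drug.

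The cost is a few more paused infusions, including some where dopamine is given as a vasopressor; the documents give no figure for how many. Dobutamine and milrinone timing is already needed for outcome 7a, so dopamine start time is the only new data item.
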